### 10.1.2 Visit windows

For visit-based variables (for visits see schedule of assessments in [Table 1](#) and [Table 2](#)), analysis windows are based on study day numbers defined as follows:

**Study day** is defined for the entire study as assessment date minus randomization date plus 1 day. Thus, the day of randomization is study Day 1. For dates prior to randomization, study day is the negative number of days between the date under consideration and the date of randomization. Thus, the day before randomization date is study Day –1. Study Day 0 does not exist.

**Withdrawal (WD)** day is defined for the DB-WD part as assessment date minus re-randomization date plus 1 day. If a subject is not re-randomized, then WD day is not defined.

The analysis windows around the visits are given in [Table 6](#). For efficacy variables (except for ABPM measurements) and safety analyses the windows are based on study or WD days and on the start and stop dates of the study parts defined above.

**Table 6 Visit windows**

Visit	Target		Efficacy		Safety	
	Study day	WD day	Lower a	Upper a	Lower a	Upper a
DB part						
4 (Randomization)	1	-		1		1
5 (Week 2)	14	-	8	20	2	20
6 (Week 4)	28	-	21	36 b	21	36 b
SB aprocitentan part						
7 (Week 6)	42	-	37 c	62	37 c	62
8 (Week 12)	84	-	63	111	63	111
9 (Week 20)	140	-	112	167	112	167
10 (Week 28)	198	-	168	223	168	223
11.1 (Week 36)	252	-	224	258 d	224	258 d
DB-WD part						
11.2 (Re-randomization)	-	1		1		1
12 (Week 38)	266	14	8	20	2	20
13 (Week 40)	280	28	21	41	21	41
14 (Week 44)	308	56	42	69	42	69
15 (Week 48)	336	84	70	97	70	97 e
EOS (EOT + 30 days)	366	114	NA	NA	98	

a vs study day for the DB part and vs WD day for DB-WD part. b Or end of DB treatment part + one day (whichever comes first). c But not before start of SB aprocitentan part (whichever comes first). d Or end of SB aprocitentan part + one day (whichever comes first). e Or end of DB-WD treatment part + one day (whichever comes first).  
 DB = double-blind; NA=Not applicable; WD = withdrawal.

If there is more than one value within the same visit window, the value closest to the planned assessment date will be taken. Where multiple assessments fall on the same day or have the same visit label, then the latest in time is used (or with the highest SDTM sequence number, if time is not collected). In the event of equidistant values from the planned time point, the last assessment will be considered for the analyses. If there are records ‘on-treatment’ and ‘off treatment’ within the same visit window, use only those ‘on-treatment’.

If measurements involve time, the following target times should be considered:

- Target day/time = Target day and time 12:00
- Lower day/time = Lower day and time 0:00
- Upper day/time = Upper day and time 23:59

AOBPM measurements (efficacy) will also have indicator whether the measurement was ‘on-treatment’. A measurement is considered on-treatment if it was taken before or within one day of the end of the randomized treatment period (defined above).

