### 6.5.2 Analyses

All other efficacy variables will be tested at the two-sided significance level of 0.05. No correction for multiplicity will be applied.

- *Changes from baseline to Week 2 of DB treatment in mean trough SiSBP and SiDBP measured by AOBPM* will be analyzed using the mixed model described for changes from baseline to Week 4 in mean trough SiSBP and SiDBP, respectively.
- *Changes from baseline to Week 4 in daytime and nighttime mean SBP and DBP measured by ABPM* will be analyzed in the aFAS using the same ANCOVA as described for 24 h mean SBP and DBP.
- *Changes from DB-WD baseline (Week 36) to Week 38 of DB-WD treatment in mean trough SiSBP and SiDBP measured by AOBPM* will be analyzed in the mFAS using the mixed model described for changes from DB-WD baseline (Week 36) to Week 40 in mean trough SiSBP and SiDBP, respectively.

- *Changes from DB-WD baseline (Week 36) to Weeks 40 and 48 of DB-WD treatment in mean trough SiSBP/SiDBP measured by AOBPM will be analyzed in the mFAS using the same mixed model, extended with Week 44 and Week 48.*
- *Changes from DB-WD baseline (Week 36) to Week 40 in daytime and nighttime mean SBP and DBP measured by ABPM will be analyzed in the mFAS using the same ANCOVA as described for 24 h mean.*
- *Ratios to baseline (and DB-WD baseline [Week 36] as applicable) for all assessed time points of DB+SB and DB-WD parts in UACR will be log transformed and analyzed using a mixed model with a factor for treatment group, visit, treatment by visit interaction, covariates for baseline (DB-WD baseline [Week 36]) log UACR and visit by baseline (DB-WD baseline [Week 36]) interaction and an unstructured covariance matrix. This will be done separately for the DB+SB part on the FAS and for the DB-WD part on the mFAS.*

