- *The number (%) of subjects who discontinued study treatment due to lack of efficacy will be tabulated by study part (DB, SB aprocitentan and DB-WD) and treatment group (within study part) in the FAS (2×) and mFAS, respectively. If there are at least 12 subjects discontinued due to lack of efficacy, time from Randomization to treatment discontinuation due to lack of efficacy in the DB or SB aprocitentan part will be summarized by treatment group using Kaplan-Meier plots in the FAS. For subjects who did not discontinue treatment or discontinued treatment for reasons other than lack of efficacy, time to discontinuation will be censored at the last dose of DB or SB treatment (whichever comes last). Additionally, a ‘two-step’ Cox model with a factor for treatment will be fitted [see Section 8.2 for details]. Time from Re-randomization to treatment discontinuation due to lack of efficacy in the DB-WD part will be summarized similarly in the mSAF, except that the Cox model is the conventional one. For subjects who did not discontinue treatment or discontinued treatment for reasons other than lack of efficacy in the DB-WD part, time to discontinuation will be censored at the last DB-WD treatment + 30 days (or EOS date, whichever comes first).*
- *The number (%) of subjects who initiated antihypertensive rescue medication will be summarized by study part (SB and DB-WD; rescue medication is not allowed in the DB part) and treatment group (within study part).*
- *Home SBP/DBP collected due to the COVID-19 pandemic will be summarized by visit in DB, SB and DB-WD parts using descriptive statistics.*
- *The number (%) of subjects with SBP/DBP Control will be tabulated for the DB+SB and DB-WD parts at each visit by treatment group in the FAS and mFAS, respectively. Subjects with a missing value at a given visit will be excluded from the analysis at that visit. The Cochran-Mantel-Haenszel (CMH) test will be used to test for a difference in the Control proportions at Week 4 between treatment groups in DB part on the FAS and at Week 40 between treatment groups in DB-WD part (stratified by randomized*

treatment in the DB part) on the mFAS. The treatment effect will be expressed in terms of the aprocitentan to placebo OR and corresponding 95% CI. An OR > 1 will indicate a benefit of aprocitentan as compared to placebo.

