## 7.3 Laboratory tests

### 7.3.1 Variables

Laboratory assessments are performed according to the schedule of assessments [Table 1 and Table 2]. Laboratory data are evaluated in SI units as provided by the central laboratory. The following tests are considered:

- Hematology: hemoglobin, hematocrit, erythrocyte count, reticulocyte count, leukocyte count with differential counts, platelet count, mean corpuscular volume.
- Clinical Chemistry: aminotransferases (aspartate aminotransferase [AST] / alanine aminotransferase [ALT]), alkaline phosphatase, bilirubin and direct bilirubin, cholesterol, triglyceride, high density lipoprotein, low density lipoprotein, creatinine, eGFR (estimated using the CKD-EPI creatinine equation), urate, albumin, protein, glucose, sodium, potassium.
- Urinalysis: UACR.

For women of childbearing potential, urine as well as serum pregnancy tests are performed, but these results will not be summarized as part of the laboratory data. Positive pregnancy tests (if any) will be reported.

Results of local laboratory tests (collected on the **Local Laboratory Hematology** and **Local Laboratory Clinical Chemistry** eCRF) will not be used in summaries but will be listed.

Laboratory marked abnormalities are defined in Section 14.2. When determining double-blind treatment-emergent marked laboratory abnormalities, all assessments (including the unscheduled ones) are considered.

All assessments (including the unscheduled ones) are considered and re-assigned to the most appropriate visit according to the rules described in Section 10.1.2.

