## 7.4 Electrocardiography

### 7.4.1 Variables

A standard 12-lead ECG is performed as defined in the schedule of assessments [[Table 1](#) and [Table 2](#)]. ECG data will be electronically transferred from the ECG laboratory database to Idorsia and will not be (re-)calculated.

The following variables will be evaluated: HR (bpm), PR (ms), QRS (ms), QT (ms), QTcB (ms), and QTcF (ms). Note that HR will be evaluated only in the context of the ECG. For vital signs, pulse rate will be used based on assessment done during AOBPM.

ECG abnormalities are defined as follows:

- QTcF (Fridericia's formula) maximum value > 450 ms, > 480 ms, or > 500 ms;
- Maximum increase from baseline in QTcF (Fridericia's formula) > 30 ms, > 60 ms.

All assessments (including the unscheduled ones) are considered and re-assigned to the most appropriate visit according to the visit windows described in [Section 10.1.2](#).

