## 7.5 Vital signs and body weight

### 7.5.1 Variables

Body weight and pulse rate (this term is used to distinguish it from heart rate measured by ECG) are assessed according to the schedule of assessments [Table 1 and Table 2]. Pulse rate is measured simultaneously with AOBPM and the average of four readings (calculated by the vendor) will be used in the analysis. All assessments (including the unscheduled ones) are considered and re-assigned to the most appropriate visit according to the visit windows described in Section 10.1.2.

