**Table 5 Summary of safety analyses**

Endpoint	Part	Analysis set	Visits	Statistical analysis (if applicable)
Adverse events	DB	SAF	NA	
	SB	rSAF	NA	
	DB-WD	mSAF	NA	
Serious adverse events	DB	SAF	NA	
	SB	rSAF	NA	
	DB-WD	mSAF	NA	
Adverse events leading to treatment discontinuation	DB	SAF	NA	
	SB	rSAF	NA	
	DB-WD	mSAF	NA	
Adverse event of special interest	DB	SAF	NA	
	SB	rSAF	NA	
	DB-WD	mSAF	NA	
Laboratory values and changes from baseline	DB+SB	SAF	Week 4, 6, 12, 20, 28 and 36	
Laboratory values and changes from DB-WD baseline (Week 36)	DB-WD	mSAF	Week 40, 44 and 48	
Number (%) of subjects with marked abnormalities laboratory values	DB,	SAF	NA	
	SB	rSAF		
	DB-WD	mSAF	NA	
Vital signs values and changes from baseline over time	DB+SB	SAF	Week 2 up to Week 36	
Vital signs values and changes from DB-WD baseline (Week 36) over time	DB-WD	mSAF	Week 38 up to Week 48	
ECG values over time and changes from baseline over time	DB+SB	SAF	Week 2 up to Week 36	

Endpoint	Part	Analysis set	Visits	Statistical analysis (if applicable)
ECG values over time and changes from DB-WD baseline (Week 36) over time	DB-WD	mSAF	Week 48	
Number (%) of subjects with marked abnormalities ECG values	DB	SAF	NA	
	SB	rSAF		
	DB-WD	mSAF	NA	
MACE-plus	DB+SB	SAF	NA	Cox model
	DB-WD	mSAF	NA	Cox model
MACE-plus	All	SAF	NA	Incidence rate
Increase or addition of diuretic	DB+SB	SAF	NA	Cox model
	DB-WD	mSAF	NA	Cox model

DB = double-blind; DB-WD = double-blind withdrawal; ECG = electrocardiogram; MACE = major adverse cardiac event; mSAF = modified Safety analysis set; NA = Not applicable as not by visit; NT-proBNP = N-Terminal pro-brain natriuretic peptide; rSAF = restricted Safety analysis set; SAF = Safety analysis set; SB = single-blind.

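### The Week 36 analysis window closes at Day 258, although the schedule allows Visit 11 up to Day 264

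*SAP*

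**What the plan says.** SAP Table 2 schedules Visit 11 (Week 36) at Day 252 with a tolerance of 12 days either side. SAP Section 10.1.2, Table 6, gives the matching analysis window as "11.1 (Week 36) 252 - 224 258 d", with the same limits for efficacy and safety. Footnote d on the upper limit reads "Or end of SB aprocitentan part + one day (whichever comes first").

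These windows decide which visit a value belongs to:

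- Laboratory values (Section 7.3.1) are "re-assigned to the most appropriate visit according to the rules described in Section 10.1.2".
- ECG values (Section 7.4.1) and weight and pulse rate (Section 7.5.1) follow the same rule: "re-assigned to the most appropriate visit according to the visit windows described in Section 10.1.2".

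Week 36 is a reported time point. Table 5 lists the DB+SB laboratory visits as "Week 4, 6, 12, 20, 28 and 36". In Section 6.5.2, UACR ratios "for all assessed time points of DB+SB and DB-WD parts in UACR will be log transformed" and analysed in a mixed model, and blood pressure control "will be tabulated for the DB+SB and DB-WD parts at each visit by treatment group".

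Two other provisions bear on a late Visit 11. Section 10 defines the DB-WD baseline as the latest value up to the day of re-randomisation, with no Day 258 limit. The COVID-19 addendum (Section 2.1.1) lets Visit 11 run from 12 days early to 8 weeks late, and its introduction says such measures remain protocol deviations.

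**The concern.** The window is narrower than the schedule it serves. A subject seen on Days 259 to 264 has complied with the visit schedule, yet the value falls in no single-blind row of Table 6.

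Week 36 closes the 32-week single-blind part, and long-term safety is a stated secondary objective. A late but compliant subject would drop out of the Week 36 DB+SB results for laboratory values, plasma volume, ECG, weight, pulse rate, UACR and blood pressure control and response. If the subject also has an unscheduled value on Days 224 to 258, that earlier value would be reported as Week 36 in place of the real visit. A subject who is not re-randomised has no withdrawal day, so the late value fits no row at all.

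**Working it through.** **Where Day 258 probably comes from.** The SAP does not say, but most limits in Table 6 follow a midpoint rule: the upper limit is the midpoint between two adjacent visit days, less one day.

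- Week 36: (252 + 266)/2 − 1 = 258, as stated.
- Weeks 2, 6, 12, 20 and 28: 20, 62, 111, 167 and 223, all as stated. This uses Table 2's Day 196 for Week 28; Table 6 prints 198 as the target.
- Week 4 departs from the rule: 34 by midpoint, 36 stated.
- The Week 36 lower limit also fits: (196 + 252)/2 = 224.

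**Schedule against window, visits placed by study day** (Table 2 day ± tolerance against the Table 6 day limits):

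| Visit | Table 2 days | Table 6 window | Scheduled days outside |
|---|---|---|---|
| 5 (Week 2) | 12–16 | 8–20 | 0 |
| 6 (Week 4) | 26–30 | 21–36 | 0 |
| 7 (Week 6) | 40–44 | 37–62 | 0 |
| 8 (Week 12) | 74–94 | 63–111 | 0 |
| 9 (Week 20) | 130–150 | 112–167 | 0 |
| 10 (Week 28) | 186–206 | 168–223 | 0 |
| 11 (Week 36) | 240–264 | 224–258 | 6 (259–264) |

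For Visit 11 the permitted days number 264 − 240 + 1 = 25, of which 264 − 258 = 6 lie outside. The permitted days after target are 253 to 264, so 6 of 12.

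**Withdrawal visits.** Visits 12 to 15 are placed by withdrawal day. The four target pairs in Table 6 imply one anchor: 266 − 14 + 1 = 280 − 28 + 1 = 308 − 56 + 1 = 336 − 84 + 1 = Day 253. Relative to re-randomisation on Day 253, the scheduled ranges are withdrawal Days 10–18, 24–32, 52–60 and 80–88. All lie within their windows (8–20, 21–41, 42–69, 70–97). This depends on the anchor: if the visits stayed at fixed study days while re-randomisation moved over Days 241 to 265, Visit 12 could fall anywhere from withdrawal Day −2 to 30, and the other three could also leave their windows.

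**Can other text recover Days 259 to 264?**

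- Footnote d takes the earlier of two dates, so it cannot extend the window.
- Row 11.2 (re-randomisation) has no lower limit and would hold the value, but it belongs to the withdrawal part and needs a withdrawal day. No text carries it into the DB+SB summaries.
- The rule in Section 10.1.1 on gap days assigns days to a study part, not to a visit.

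**Addendum.** The latest permitted day is 252 + 56 = 308. Of the 308 − 240 + 1 = 69 permitted days, 308 − 258 = 50 lie outside row 11.1. The addendum's wider ranges for Visits 6 to 10 all stay inside Table 6.

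**Check of the remedy.** Take Visit 11 on Day 264 and re-randomisation on Day 265. The present limit of 258 loses the value. A limit at the earliest of Day 264, end of single-blind treatment plus one day, and withdrawal Day 1 (Day 265) is Day 264 if single-blind dosing runs to at least Day 263, and the value is kept. The safety Week 38 window opens at withdrawal Day 2, Day 266, so there is no overlap.

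**The case against.** The strongest reply is that Day 258 is no slip: it follows the midpoint rule used almost throughout Table 6. That explains why the window reaches 28 days before target and only 6 after. It also makes a comparison with the 20 to 27 days allowed after Visits 7 to 10 weak evidence, because those visits are followed by gaps of 42 or 56 days and Week 36 by a gap of 14. This stands as an account of the number, but it does not justify the cap. A midpoint separates two windows on the same clock, and Week 38 is placed by withdrawal day. No study-day row competes for Days 259 to 264.

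Several limits on the weight of the point also stand:

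- For re-randomised subjects the late value still serves as DB-WD baseline, and all safety data are listed.
- Adverse events and laboratory marked abnormalities are assigned by study part, so they do not depend on this row. ABPM is outside the efficacy windows.
- Control and response are tested only at Weeks 4 and 40, so Week 36 is tabulated only. Week 36 UACR is one visit in an exploratory model.
- Only an unscheduled assessment could supply a substitute value from early in the window: scheduled Visit 10 ends at Day 206, or Day 217 under the addendum.
- Six of 25 is a count of days, not a share of subjects.

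Finally, Day 264 recovers only 6 of the 50 uncovered days under the addendum. Dropping the fixed limit and keeping only the end-of-treatment cap would cover all of them, provided treatment runs up to the visit. That is workable, but it would put values up to 56 days late into the main Week 36 summary.

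**Conclusion.** The concern holds. Table 2 and Table 6 disagree for Visit 11 and for no other visit placed by study day. Six of 25 in-schedule days have no Week 36 slot in the DB+SB summaries, and nothing else in the SAP supplies one.

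The consequence is limited to descriptive and exploratory Week 36 results. The primary, key secondary and ABPM analyses, adverse events and laboratory marked abnormalities do not change. The documents give no distribution of visit timing, so the number of subjects is unknown and could be small. The group with no row at all, those with a late Visit 11 who were not re-randomised, is likely narrow.

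The conclusion rests on reading the windows and footnote d literally. It is worth correcting because the rule as written drops or replaces compliant end-of-part values, and the correction costs little.

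**What to change.** In Table 6, row 11.1, raise the efficacy and safety upper limits from Day 258 to Day 264. Keep the cap in footnote d and add that, for re-randomised subjects, the window ends no later than withdrawal Day 1. If Day 258 is intended, state the reason in Section 10.1.2.

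For Visit 11 held after Day 264 under the addendum, report the number of subjects and show Week 36 with them included as a supportive summary only.

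The cost is two limits and one footnote, plus one count and one supportive summary. It needs no new data, and neither the visit schedule nor the primary or key secondary analysis changes. Two limitations remain. Some Week 36 values will be up to 12 days later than nominal. The existing closest-to-target rule will also still prefer an unscheduled value nearer Day 252 where one exists, as it does at every other visit.

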 Study treatment including standardized background antihypertensive therapy should be brought back at each visit for drug accountability (pill counts).

 All AEs and SAEs that occur after signing the informed consent form and up to 30 days after study treatment discontinuation must be reported.

 Randomized subjects who prematurely discontinue prior to Week 48/Visit 15 should have an EOT visit scheduled no later than 7 days after the last dose of randomized study treatment.

 For subjects who discontinued during the RI period, this will be a phone call to collect adverse events and concomitant medications only.

ABPM = ambulatory blood pressure monitoring; AE = adverse event; AOBPM = automated office blood pressure measurement; BP = blood pressure; DB = double-blind; ECG = electrocardiogram; EOS = End-of-Study; EOT = End-of-Treatment; FU = follow-up; HR = heart rate; NT-proBNP = N-terminal pro-brain natriuretic peptide; PK = pharmacokinetic(s); RI = run-in; SAE = serious adverse event; SB = single-blind; UACR = urine albumin-to-creatinine ratio; WD = withdrawal.

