### 6.2.2 Intercurrent events and choice of estimand

There are two types of intercurrent events that may interfere with the analysis of the primary endpoint: premature discontinuation of DB treatment or the addition / dose increase of a diuretic. Use of rescue medication, although not allowed during the DB part, will be also considered as an intercurrent event.

All AOBPM measurements, irrespective of any intercurrent event(s), will be included in the main analysis, leading to a treatment policy strategy estimand in ICH terminology [ICH 2017b].

Based on the Phase 2 study in essential hypertension, AC-080A201, it is expected that 5% of subjects in the FAS will have a missing Week 4 AOBPM, mainly due to premature treatment discontinuation. In the main analysis [Section 6.2.3] missing data will not be imputed but will be handled by a mixed model assuming that the data are MAR. Sensitivity analyses will be performed, investigating the impact of deviations from MAR as well as considering a different estimand [Section 6.2.4].

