Change from baseline to Week 4 in mean nighttime DBP	ABPM		ANCOVA	aFAS	Week 4	Included
Change from DB-WD baseline (Week 36) to Week 38 in SiSBP	AOBPM		Mixed model (key secondary)	mFAS	Weeks 38,40	Included
Changes from DB-WD baseline (Week 36) to Weeks 44 and 48 in SiSBP	AOBPM		Mixed model	mFAS	Weeks 38,40, 44, 48	Included
Changes from DB-WD baseline (Week 36) to Week 38 in SiDBP	AOBPM		Mixed model	mFAS	Weeks 38,40	Included

Endpoint	Measured by	Analysis	Model	Analysis set	Visits	Data after intercurrent event*
Changes from DB-WD baseline (Week 36) to Weeks 44 and 48 in SiDBP	AOBPM		Mixed model	mFAS	Weeks 38,40, 44, 48	Included
Change from DB-WD baseline (Week 36) to Week 40 in mean daytime SBP	ABPM		ANCOVA	maFAS	Week 40	Included
Change from DB-WD baseline (Week 36) to Week 40 in mean nighttime SBP	ABPM		ANCOVA	maFAS	Week 40	Included
Change from DB-WD baseline (Week 36) to Week 40 in mean daytime DBP	ABPM		ANCOVA	maFAS	Week 40	Included
Change from DB-WD baseline (Week 36) to Week 40 in mean nighttime DBP	ABPM		ANCOVA	maFAS	Week 40	Included
Ratio to baseline of UACR			Mixed model	FAS	Week 2 up to Week 36	Included
Ratio to DB-WD baseline (Week 36) of UACR			Mixed model	mFAS	Week 38 up to Week 48	Included
Time from Randomization to discontinuation of study treatment due to lack of efficacy			Cox model (two-step)	FAS	NA	NA
Time from Re-randomization to discontinuation of study treatment due to lack of efficacy			Cox model	mFAS	NA	NA

\* In the DB part: Premature DB treatment discontinuation or addition / dose increase of diuretic (whichever comes first); in the DB-WD part: Premature DB-WD treatment discontinuation, initiation of antihypertensive rescue medication or addition / dose increase of diuretic (whichever comes first).

ABPM = ambulatory blood pressure monitoring; aFAS = ABPM Full analysis set; ANCOVA = analysis of covariance; AOBPM = automated office blood pressure measurement; CR = Copy Reference; DB = double-blind; DBP = diastolic blood pressure; FAS = Full analysis set; J2R = Jump to Reference; LOCF = last observation carried forward; maFAS = modified ABPM Full analysis set; mFAS = modified Full analysis set; mPPS = modified Per-Protocol set; NA = not applicable; PPS = Per-Protocol Set; SiDBP = (mean trough) sitting diastolic blood pressure; SiSBP = (mean trough) sitting systolic blood pressure; UACR = urine albumin-to-creatinine ratio; WD = withdrawal.

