### 10.1 Analysis periods and visit windows

#### 10.1.1 Analysis periods

The **screening period** is defined as the time from the informed consent date until one day before the run-in period start date (or EOS if the subject does not enter the run-in).

The **RI period** begins at the date of the first dose of RI treatment and ends at the date of the last dose of RI treatment, collected on the **Study Treatment Log** where ‘Study Period’ is ‘Single Blind Run-in’.

The **randomized treatment period** begins at the DB treatment start date and ends at the *last* of the treatment stop dates collected on the **Study Treatment Log** where ‘Study Period’ is not ‘Single Blind Run-in’ and the reason for treatment end is not ‘Interruption due to an AE’ or ‘Interruption not due to an AE’.

The randomized treatment period is divided into three parts: DB, SB aprocitentan and DB-WD.

- The DB part begins at the DB treatment start date and ends at the DB treatment stop date collected on the **Study Treatment Log** where ‘Study Period’ is ‘Double-Blind Treatment (Part 1)’ and the reason for treatment end is not ‘Interruption due to an AE’ or ‘Interruption not due to an AE’.
- The SB aprocitentan part begins at the SB treatment start date and ends at the SB treatment stop date collected on the **Study Treatment Log** where ‘Study Period’ is ‘Single-Blind Treatment (Part 2)’ and the reason for treatment end is not ‘Interruption due to an AE’ or ‘Interruption not due to an AE’.
- The DB-WD part begins at the DB-WD treatment start date and ends at the DB-WD treatment stop date collected on the **Study Treatment Log** where ‘Study Period’ is ‘Double-Blind Withdrawal Treatment (Part 3)’ and the reason for treatment end is not ‘Interruption due to an AE’ or ‘Interruption not due to an AE’.

Should there be any ‘gap’ between the end of one period and the start of the next, then the gap days are allocated to the former period. In the unlikely case that the gap is more than 30 days, gap days 31, 32, etc. will not be allocated to a study part.

The **safety FU period** begins one day after the end of the randomized treatment period and ends at the date of the EOS visit. Safety data obtained during the safety FU period or at the EOS visit will be allocated to the last part of the subject’s randomized treatment period. This is restricted to data collected up to EOT+30 days. Safety data collected beyond that time point will not be allocated to a study part.

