- All AOBPM measurements obtained after premature discontinuation of DB or DB-WD treatment or the addition/dose increase of a diuretic will be included in the main analysis, leading to a treatment policy strategy estimand in ICH terminology [ICH 2017b].

A hypothetical strategy estimand will be used in sensitivity analyses [see Sections 6.5.1 and 6.3.4 of this SAP].

Endpoints related to BP control and response were added as exploratory endpoint [see Sections 6.5.1 and 6.5.2 of this SAP].

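### For subjects who stop double-blind treatment early and never enter the single-blind part, Table 6 footnote b removes Day 21–36 readings from Week 4, contradicting the treatment-policy primary analysis

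*SAP*

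**What the plan says.** SAP 6.2.2 sets the data rule for the primary endpoint: "All AOBPM measurements, irrespective of any intercurrent event(s), will be included in the main analysis". Section 11, which records the move away from the hypothetical strategy, repeats it: "All AOBPM measurements obtained after premature discontinuation of DB or DB-WD treatment or the addition/dose increase of a diuretic will be included". Table 4 marks data after an intercurrent event as included in the main analysis, and its footnote defines those events: "In the DB part: Premature DB treatment discontinuation or addition / dose increase of diuretic".

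Readings reach the model through visit windows. SAP 10.1.2 says that, for efficacy variables other than ABPM, "the windows are based on study or WD days and on the start and stop dates of the study parts defined above". In Table 6 the Week 4 efficacy window is Day 21 to Day 36, and footnote b to the upper limit reads "Or end of DB treatment part + one day (whichever comes first". SAP 10.1.1 fixes the end of the DB part: "The DB part begins at the DB treatment start date and ends at the DB treatment stop date".

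Readings after an early stop are planned. Under Table 2, footnote 11, subjects who discontinue early "should have an EOT visit scheduled no later than 7 days after the last dose of randomized study treatment", and AOBPM is scheduled at that visit.

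**The concern.** Sections 6.2.2 and 11 and Table 4 keep post-discontinuation readings, while footnote b gives some of them no Week 4 slot. The cut-off is the one that footnote 1 of SAP 6.2.4 uses for the hypothetical-strategy analysis: a reading on the day after the last dose stays in, and one a day later is out. For treatment discontinuation, the main analysis and the analysis meant to contrast with it would then share the same Week 4 cut.

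The treatment-policy estimand was adopted after regulatory comments, and 6.2.2 names early discontinuation as the main expected cause of a missing Week 4 value. Turning collected readings into missing ones, handled under MAR, undoes part of that change. If the BP effect fades quickly after stopping, as 6.2.4 anticipates, the estimate moves in favour of aprocitentan.

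**Working it through.** The plan gives no figure for this point, so the check is date arithmetic.

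**Inputs.** Let x be the study day of the last DB dose, for a subject who never enters the SB part.
- Week 2 efficacy window: Days 8–20, no cap (Table 6).
- Week 4 efficacy window: Day 21 to min(36, x+1) (Table 6 footnote b with 10.1.1).
- Permitted end-of-treatment (EOT) visit: taken as Days x+1 to x+7 (Table 2 footnote 11).
- Visit 6: Day 28 ±2, so Days 26–30 (Table 2); ±1 week, so Days 21–35, under the COVID-19 addendum, section 2.1.1.

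**Does any other rule extend the window?**
- The gap rule in 10.1.1 gives days between two periods to the earlier one. For these subjects the next period is safety follow-up, which starts the day after treatment ends. There is no gap.
- The follow-up re-allocation in the same section is limited: "Safety data obtained during the safety FU period or at the EOS visit will be allocated to the last part". It does not cover efficacy AOBPM.
- No text says that 6.2.2 overrides Table 6.

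**Permitted EOT days dropped from Week 4 by footnote b** (Day x+2 or later and within Days 21–36):

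| Last dose x | Dropped per x | Total | Week 4 status |
|---|---|---|---|
| 1–13 | 0 | 0 of 91 | EOT falls by Day 20, so the lower limit, not footnote b, keeps it out |
| 14–19 | 1, 2, 3, 4, 5, 6 | 21 of 42 | Always empty, since x+1 ≤ 20 |
| 20–24 | 6 each | 30 of 35 | Empty unless a reading falls in Day 21 to x+1 |
| 25–27 | 6 each | 18 of 21 | A Visit 6 reading by Day x+1 may already fill it |

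For x = 14–27 the total is 21 + 30 + 18 = 69 of 6×7 + 5×7 + 3×7 = 98. For x = 20–24 a Visit 6 on Days 26–30 cannot help, because x+1 is at most 25; under the addendum's wider window an early Visit 6 could.

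A wider enumeration took x = 1–35 with readings on Days x+2 to x+7, which is 35×6 = 210 pairs. As written, none reaches Week 4. With the limit held at Day 36, 96 do (x = 14–34); 78 belong to Week 2 and 36 to neither window, with or without the footnote.

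**Example.** Last dose on Day 22, EOT on Day 28, the Week 4 target day. The window closed on Day 23, so the reading has no slot.

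**Scale, on assumptions.**
- One arm is about 730/3 = 243 subjects; 1% is about 2.4. If the dropped readings differ by 4–10 mmHg from the model's prediction (assumed), the arm mean shifts by 0.01 × 4 = 0.04 to 0.01 × 10 = 0.10 mmHg per 1% affected.
- In relative terms, suppose a share f of an active arm is affected, the lost readings would have shown no effect, and MAR credits the full effect. The estimate then exceeds the treatment-policy value by 1/(1−f) − 1: 1.0%, 3.1% and 5.3% for f = 1%, 3% and 5%.
- Section 6.2.2 expects 5% of subjects to lack a Week 4 value. Applied to the 730 randomized, that is 0.05 × 730 = 36.5, about 12 per arm. This covers all causes and only indicates the order of magnitude.

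**The case against.** The declared intent is clear and stated three times, and footnote b reads like a boundary rule meant to keep SB readings out of Week 4. The rule in 10.1.2 that prefers on-treatment to off-treatment readings within a window also presumes that off-treatment readings can be there. This makes an oversight likely. It does not remove the conflict, because programming works from Table 6 and nothing gives 6.2.2 precedence.

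Several narrower objections stand:
- Day counts are not subject counts. They weight every stop day and visit day equally.
- For x = 25–27 an on-treatment Visit 6 reading may already fill the window, and the preference rule would then discard the later reading anyway.
- The direction is conditional: antihypertensives started after stopping also count under treatment policy and could lower those readings.
- The 4–10 mmHg is assumed.
- Week 40 has no such cap although 6.3.2 declares the same strategy, but it is not at a part boundary, so the contrast adds little.

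The J2R, CR, tipping-point and BOCF analyses do probe departures from MAR for these missing values. They impute where a reading was collected, so they cover the problem only in part. The available protocol text is the COVID-19 addendum, so whether early discontinuers attend any further visit between EOT and end of study cannot be checked.

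**Conclusion.** The concern holds. Read literally, Table 6 does not deliver the declared primary estimand at Week 4 for subjects who stop DB treatment and do not enter the SB part. Confidence is high for the contradiction and the date arithmetic, and lower for impact. The effect is probably small, the number affected is unknown, and the direction favours aprocitentan only if the BP effect is lost after stopping. It should be fixed because it decides which observed data enter the primary analysis.

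The finding is confined to Week 4 readings on Days 21–36. Footnote b does not cut Week 2, Week 40, or readings after a diuretic change or rescue medication while DB treatment continues. End-of-study readings are left aside because Table 6 lists their efficacy window as not applicable.

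**What to change.** - In the efficacy column of Table 6, limit footnote b to subjects who enter the SB part, and leave it unchanged for them.
- For subjects who do not enter the SB part, let the Week 4 window run to Day 36 in the treatment-policy analyses.
- The not-applicable entry for end of study can stay. For x = 1–6 a visit on Days x+30 to x+33 can fall on Days 31–36, so say explicitly that such a reading is not a Week 4 value.
- Keep the cut at one day after the last dose for the hypothetical-strategy analysis, using the on-treatment flag already defined in 10.1.2.
- State how the on-treatment preference works in the treatment-policy analyses: a lone off-treatment reading in the window is used, and the choice when both kinds are present is specified consistently with 6.2.2 and 6.3.2.
- Report by arm how many post-discontinuation readings enter Week 4.

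The cost is one footnote, short clarifying text and the related programming. No new data or visits are needed. The estimate may become slightly less favourable.
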